APPENDIX C

Bexarotene Gel Diaries

Bexarotene Gel Diary [IRB Protocol #:]

Group 1

PID: _____

Amount of Agent Provided: Number of Canisters _____

Total Daily Dose: 10mg applied to one breast, **every other day**

Pump actuations: Push the Pump 1 time

Breast to Apply Gel: Right OR Left

Number of Canisters Returned: _____

Visit#: _____

INSTRUCTIONS:

1. Complete the diary daily.
2. If you miss an application, do not take an extra application to “make up” for the missed application.

If your next dose is scheduled within the next 24 hours, it is best just to wait; if it is more than 24 hours until your next dose, apply the dose you missed and resume your normal dosing after that.
3. If you accidentally pump more than is needed for one breast, please discard this dose and try again to get correct dose. If you do discard pumped doses, please record this on your Gel Diary.
4. Do not discard the gel canister. Bring the canister and this diary to your next appointment.
5. Store the study gel at home at room temperature and avoid extreme heat or cold during transportation from the clinic to home.
6. If you experience any concerning side effects or changes in the texture of your skin (e.g., skin feels like sandpaper), call _____ (insert name of Study Coordinator or Study Nurse) at _____ (insert telephone number) or the study doctor, [name] at [contact] for guidance.

Bexarotene Gel Diary Group 1 Continued

Please Bring this Sheet and Empty Canister to Your Next Visit

	Day	Date	R or L Breast, OR Did not apply	Initials	Did you experience any symptoms, if "Yes" list below List # of discarded pumps of gel here
Week 1 Apply 1 pump to the breast every other day	1		 R  L  Did not apply		
	2		 R  L  Did not apply		
	3		 R  L  Did not apply		
	4		 R  L  Did not apply		
	5		 R  L  Did not apply		
	6		 R  L  Did not apply		
	7		 R  L  Did not apply		
Week 2 Apply 1 pump to the breast every other day	8		 R  L  Did not apply		
	9		 R  L  Did not apply		
	10		 R  L  Did not apply		
	11		 R  L  Did not apply		
	12		 R  L  Did not apply		
	13		 R  L  Did not apply		
	14		 R  L  Did not apply		
Week 3 Apply 1 pump to the breast every other day	15		 R  L  Did not apply		
	16		 R  L  Did not apply		
	17		 R  L  Did not apply		
	18		 R  L  Did not apply		
	19		 R  L  Did not apply		
	20		 R  L  Did not apply		
	21		 R  L  Did not apply		

	Day	Date	R or L Breast, OR Did not apply	Initials	Did you experience any symptoms, if "Yes" list below List # of discarded pumps of gel here
Week 4 Apply 1 pump to the breast every other day	22		 R  L  Did not apply		
	23		 R  L  Did not apply		
	24		 R  L  Did not apply		
	25		 R  L  Did not apply		
	26		 R  L  Did not apply		
	27		 R  L  Did not apply		
	28		 R  L  Did not apply		
	29		 R  L  Did not apply		
	30		 R  L  Did not apply		

Participant's Signature: _____

Date: _____

Reviewer's Signature: _____

Date: _____

Comments:

Bexarotene Gel Diary [IRB Protocol #: _____]

Group 2

PID: _____

Amount of Agent Provided: Number of Canisters _____

Total Daily Dose:

Week 1: 10mg applied to one breast, **every other day**
Push the Pump 1 time

Weeks 2-4: 10mg applied to one breast, **every day**
Push the Pump 1 time

Breast to Apply Gel: Right OR Left

Number of Canisters Returned: _____

Visit#: _____

INSTRUCTIONS:

1. Complete the diary daily.
2. If you miss an application, do not take an extra application to “make up” for the missed application.

If you are applying the gel daily: If your next dose is scheduled within the next 12 hours, it is best just to wait; if it is more than 12 hours until your next dose, apply the dose you missed and resume your normal dosing after that.

If you are applying the gel every other day: If your next dose is scheduled within the next 24 hours, it is best just to wait; if it is more than 24 hours until your next dose, apply the dose you missed and resume your normal dosing after that.

3. If you accidentally pump more than is needed for one breast, please discard this dose and try again to get correct dose. If you do discard pumped doses, please record this on your Gel Diary.
4. Do not discard the gel canister. Bring the canister and this diary to your next appointment.
5. Store the study gel at home at room temperature and avoid extreme heat or cold during transportation from the clinic to home.
6. If you experience any concerning side effects or changes in the texture of your skin (e.g., skin feels like sandpaper), call _____ (insert name of Study Coordinator or Study Nurse) at _____ (insert telephone number) or the study doctor, [name] at [contact] for guidance..

Bexarotene Gel Diary Group 2 Continued
Please Bring this Sheet and Empty Canister to Your Next Visit

	Day	Date	R or L Breast, OR Did not apply	Initials	Did you experience any symptoms, if "Yes" list below List # of discarded pumps of gel here
Week 1 Apply 1 pump to the breast every other day	1		 R  L  Did not apply		
	2		 R  L  Did not apply		
	3		 R  L  Did not apply		
	4		 R  L  Did not apply		
	5		 R  L  Did not apply		
	6		 R  L  Did not apply		
	7		 R  L  Did not apply		
Week 2 Apply 1 pump to the breast every day	8		 R  L  Did not apply		
	9		 R  L  Did not apply		
	10		 R  L  Did not apply		
	11		 R  L  Did not apply		
	12		 R  L  Did not apply		
	13		 R  L  Did not apply		
	14		 R  L  Did not apply		
Week 3 Apply 1 pump to the breast every day	15		 R  L  Did not apply		
	16		 R  L  Did not apply		
	17		 R  L  Did not apply		
	18		 R  L  Did not apply		
	19		 R  L  Did not apply		
	20		 R  L  Did not apply		
	21		 R  L  Did not apply		

	Day	Date	R or L Breast, OR Did not apply	Initials	Did you experience any symptoms, if "Yes" list below List # of discarded pumps of gel here
Week 4 Apply 1 pump to the breast every day	22		 R  L  Did not apply		
	23		 R  L  Did not apply		
	24		 R  L  Did not apply		
	25		 R  L  Did not apply		
	26		 R  L  Did not apply		
	27		 R  L  Did not apply		
	28		 R  L  Did not apply		
	29		 R  L  Did not apply		
	30		 R  L  Did not apply		

Participant's Signature: _____

Date: _____

Reviewer's Signature: _____

Date: _____

Comments:

Bexarotene Gel Diary [IRB Protocol #: _____]

Group 3

PID: _____

Amount of Agent Provided: Number of Canisters _____

Total Daily Dose:

Week 1: 10mg applied to one breast, **every other day**
Push the Pump 1 time

Week 2: 10mg applied to one breast, **every day**
Push the Pump 1 time

Weeks 3-4: 20mg applied to one breast, **every day**
Push the Pump **2 times**

Breast to Apply Gel: Right OR Left

Number of Canisters Returned: _____

Visit#: _____

INSTRUCTIONS:

1. Complete the diary daily.
2. If you miss an application, do not take an extra application to “make up” for the missed application.

If you are applying the gel daily: If your next dose is scheduled within the next 12 hours, it is best just to wait; if it is more than 12 hours until your next dose, apply the dose you missed and resume your normal dosing after that.

If you are applying the gel every other day: If your next dose is scheduled within the next 24 hours, it is best just to wait; if it is more than 24 hours until your next dose, apply the dose you missed and resume your normal dosing after that.
3. If you accidentally pump more than is needed for one breast, please discard this dose and try again to get correct dose. If you do discard pumped doses, please record this on your Gel Diary.
4. Do not discard the gel canisters. Bring the canisters and this diary to your next appointment.
5. Store the study gel at home at room temperature and avoid extreme heat or cold during transportation from the clinic to home.
6. If you experience any concerning side effects or changes in the texture of your skin (e.g., skin feels like sandpaper), call _____ (insert name of Study Coordinator or Study Nurse) at _____ (insert telephone number) or the study doctor, [name] at [contact] for guidance.

Bexarotene Gel Diary Group 3 Continued

Please Bring this Sheet and Empty Canisters to Your Next Visit

	Day	Date	R or L Breast	Initials	# of pumps	Did you experience any symptoms, if "Yes" list below List # of discarded doses here
Week 1 Apply 1 pump to the breast every other day	1				___ or  Did not apply	
	2				___ or  Did not apply	
	3				___ or  Did not apply	
	4				___ or  Did not apply	
	5				___ or  Did not apply	
	6				___ or  Did not apply	
	7				___ or  Did not apply	
Week 2 Apply 1 pump to the breast every day	8				___ or  Did not apply	
	9				___ or  Did not apply	
	10				___ or  Did not apply	
	11				___ or  Did not apply	
	12				___ or  Did not apply	
	13				___ or  Did not apply	
	14				___ or  Did not apply	
Week 3 Apply 2 pumps to the breast every day	15				___ or  Did not apply	
	16				___ or  Did not apply	
	17				___ or  Did not apply	
	18				___ or  Did not apply	
	19				___ or  Did not apply	
	20				___ or  Did not apply	
	21				___ or  Did not apply	

	Day	Date	R or L Breast	Initials	# of pumps	Did you experience any symptoms, if "Yes" list below List # of discarded doses here
Week 4 Apply 2 pumps to the breast every day	22				_____ or  Did not apply	
	23				_____ or  Did not apply	
	24				_____ or  Did not apply	
	25				_____ or  Did not apply	
	26				_____ or  Did not apply	
	27				_____ or  Did not apply	
	28				_____ or  Did not apply	
	29				_____ or  Did not apply	
	30				_____ or  Did not apply	

Participant's Signature: _____

Date: _____

Reviewer's Signature: _____

Date: _____

Comments:

Bexarotene Gel Diary [IRB Protocol #:]

Dose Expansion Group

PID: _____

Amount of Agent Provided: Number of Canisters _____

Total Daily Dose: 10mg applied to one breast, **every other day**

Pump actuations: Push the Pump 1 time

Breast to Apply Gel: Right OR Left

Number of Canisters Returned: _____

Visit#: _____

INSTRUCTIONS:

1. Complete the diary daily.
2. If you miss an application, do not take an extra application to “make up” for the missed application.

If your next dose is scheduled within the next 24 hours, it is best just to wait; if it is more than 24 hours until your next dose, apply the dose you missed and resume your normal dosing after that.
3. If you accidentally pump more than is needed for one breast, please discard this dose and try again to get correct dose. If you do discard pumped doses, please record this on your Gel Diary.
4. Do not discard the gel canister. Bring the canister and this diary to your next appointment.
5. Store the study gel at home at room temperature and avoid extreme heat or cold during transportation from the clinic to home.
6. If you experience any concerning side effects or changes in the texture of your skin (e.g., skin feels like sandpaper), call _____ (insert name of Study Coordinator or Study Nurse) at _____ (insert telephone number) or the study doctor, [name] at [contact] for guidance.

Bexarotene Gel Diary: Dose Expansion Group (Continued)

Please Bring this Sheet and Empty Canister to Your Next Visit

	Day	Date	R or L Breast, OR Did not apply	Initials	Did you experience any symptoms, if "Yes" list below List # of discarded pumps of gel here
Week 1 Apply 1 pump to the breast every other day	1		 R  L  Did not apply		
	2		 R  L  Did not apply		
	3		 R  L  Did not apply		
	4		 R  L  Did not apply		
	5		 R  L  Did not apply		
	6		 R  L  Did not apply		
	7		 R  L  Did not apply		
Week 2 Apply 1 pump to the breast every other day	8		 R  L  Did not apply		
	9		 R  L  Did not apply		
	10		 R  L  Did not apply		
	11		 R  L  Did not apply		
	12		 R  L  Did not apply		
	13		 R  L  Did not apply		
	14		 R  L  Did not apply		
Week 3 Apply 1 pump to the breast every other day	15		 R  L  Did not apply		
	16		 R  L  Did not apply		
	17		 R  L  Did not apply		
	18		 R  L  Did not apply		
	19		 R  L  Did not apply		
	20		 R  L  Did not apply		
	21		 R  L  Did not apply		

	Day	Date	R or L Breast, OR Did not apply	Initials	Did you experience any symptoms, if "Yes" list below List # of discarded pumps of gel here
Week 4 Apply 1 pump to the breast every other day	22		 R  L  Did not apply		
	23		 R  L  Did not apply		
	24		 R  L  Did not apply		
	25		 R  L  Did not apply		
	26		 R  L  Did not apply		
	27		 R  L  Did not apply		
	28		 R  L  Did not apply		
	29		 R  L  Did not apply		
	30		 R  L  Did not apply		

Participant's Signature: _____

Date: _____

Reviewer's Signature: _____

Date: _____

Comments:

APPENDIX D

Alcohol and Tobacco Use Assessment Questionnaires – Baseline

ALCOHOL ASSESSMENT – BASELINE

REGISTERING INSTITUTION _____	PARTICIPANT ID _____	VISIT TYPE _____	VISIT DATE (MM/DD/YYYY) ____ / ____ / _____
----------------------------------	-------------------------	---------------------	---

Instructions:

For the following questions about drinking alcoholic beverages, a drink means a 12 oz. beer, a 5 oz. glass of wine, or one and a half ounces of liquor.

1. In your entire life, have you had at least 12 drinks of any kind of alcoholic beverage?
 Yes
 No **(End)**
 Refused **(End)**
 Don't know/Not sure
2. In the past 12 months, on average, how often did you drink any type of alcoholic beverage?
_____ (Enter the number of days you drank based on the timeframe checked below. Enter 0 if you never drank and skip to Question 6.)
 Week
 Month
 Year
 Refused
 Don't know/Not sure
3. In the past 12 months, on those days that you drank alcoholic beverages, on average, how many drinks did you have per day?
_____ (Enter the average number of drinks per day)
 Refused
 Don't know/Not sure
4. In the past 12 months, on how many days did you have 5 or more drinks of any alcoholic beverage?
_____ (Enter the number of days you had 5 or more drinks, or enter 0 if none.)
 Refused
 Don't know/Not sure
5. Was there ever a time or times in your life when you drank 5 or more drinks of any kind of alcoholic beverage almost every day?
 Yes
 No
 Refused
 Don't know/Not sure

6. If you do not currently drink alcoholic beverages, but did in the past, how long has it been since you last drank regularly?

- Within the past month (0 to 1 month ago)
- Between 1 and 3 months (1 to 3 months ago)
- Between 3 and 6 months (3 to 6 months ago)
- Between 6 and 12 months (6 to 12 months ago)
- Between 1 and 5 years (1 to 5 years ago)
- Between 5 and 15 years (5 to 15 years ago)
- More than 15 years ago
- Don't know/Not sure
- Never drank regularly

7. At the heaviest point, either now or in the past, on the days when you drank, about how many drinks did you drink a day on the average?

_____ (Enter the number of drinks a day)

- Refused
- Don't know/Not sure

8. How many years have you been drinking (or did drink) regularly?

_____ years

- Refused
- Don't know/Not sure

9. At what age did you begin drinking regularly?

_____ years of age

- Refused
- Don't know/Not sure

10. What type(s) of alcohol do you drink? (Mark ALL that apply)

- Wine
- Liquor
- Beer
- Wine cooler

Signature of Individual Completing This Form _____ Date ____ / ____ / ____
(MM/DD/YYYY)

Name of Individual Completing This Form (please print) _____

TOBACCO ASSESSMENT – BASELINE

REGISTERING INSTITUTION	PARTICIPANT ID	VISIT TYPE	VISIT DATE (MM/DD/YYYY)
_____	_____	_____	____ / ____ / _____

Section A. Basic Cigarette Use Information

1. Have you smoked at least 100 cigarettes (5 packs = 100 cigarettes) in your entire life?

- Yes
 No → **Skip to Section B**
 Don't know/Not sure → **Skip to Section B**

2. How old were you when you first smoked a cigarette (even one or two puffs)?

_____ Years old

3. How old were you when you first began smoking cigarettes regularly?

_____ Years old

Check here if you have never smoked cigarettes regularly.

4. How many total years have you smoked (or did you smoke) cigarettes? Do not count any time you may have stayed off cigarettes.

_____ Years (If you smoked less than one year, write "1.")

5. On average when you have smoked, about how many cigarettes do you (or did you) smoke a day? (A pack usually has 20 cigarettes in it).

_____ Number of cigarettes per day

6. Do you NOW smoke cigarettes?

- Everyday
 Some days
 Not at all → **Skip to question 8**

7. How soon after you wake up do you smoke your first cigarette?

- Within 30 minutes
 After 30 minutes

8. How long has it been since you last smoked a cigarette (even one or two puffs)?

First check which one of the following choices applies to you. Then, if applicable, write a number on the line for how many days, weeks, months, or years it has been since your last cigarette.

- I smoked a cigarette today (at least one puff)
- 1-7 days → Number of days since last cigarette _____
- Less than 1 month → Number of weeks since last cigarette _____
- Less than 1 year → Number of months since last cigarette _____
- More than 1 year → Number of years since last cigarette _____
- Don't know/Don't remember

Section B. Use of Other Forms of Tobacco

9. Have you ever used other forms of tobacco, not including cigarettes?

- Yes
- No → **Skip to Section C**

10. How often do you/did you use other forms of tobacco?

- Every day → Number of times per day _____
- Some days → Number of days _____ per Week Month Year

11. Which of the following products have you ever used regularly?

Check all that apply

- Cigarettes
- E-cigarettes or other electronic nicotine delivery system
- Traditional cigars, cigarillos or filtered cigars
- Pipes
- Hookah
- Clove cigarettes or kreteks
- Bidis
- Smokeless tobacco, like dip, chew, or snuff
- Snus
- Paan with tobacco, gutka, zarda, khaini
- Other, Please specify: _____

12. If you do not currently use other forms of tobacco, but did in the past, how long has it been since you last used other forms of tobacco regularly?

- Within the past month (0 to 1 month ago)
- Between 1 and 3 months (1 to 3 months ago)
- Between 3 and 6 months (3 to 6 months ago)
- Between 6 and 12 months (6 to 12 months ago)
- Between 1 and 5 years (1 to 5 years ago)
- Between 5 and 15 years (5 to 15 years ago)
- More than 15 years ago
- Don't know/Not sure
- Never used other forms of tobacco regularly

Section C. Second-Hand Smoke Exposure

13. Are you currently living with a smoker?

- Yes
- No

14. In the past 30 days, have you lived in a place where other people smoked cigarettes indoors?

- Yes
- No

15. In the past 30 days, have you worked in a place where other people smoked cigarettes indoors?

- Yes
- No

16. Thinking of all your childhood and adult years, have you ever lived in a place where other people smoked cigarettes indoors?

- Yes In total, for about how many years? _____ If less than 1, write "1."
- No

17. Thinking of all the years you have worked, have you ever worked in a place where other people smoked cigarettes indoors?

- Yes → In total, for about how many years? _____ If less than 1, write "1."
- No

Signature of Individual Completing This Form _____ Date ____/____/_____
(MM/DD/YYYY)

Name of Individual Completing This Form (please print) _____

APPENDIX E

Alcohol and Tobacco Use Assessment Questionnaires – Follow Up

ALCOHOL ASSESSMENT – FOLLOW UP

REGISTERING INSTITUTION _____	PARTICIPANT ID _____	VISIT TYPE _____	VISIT DATE (MM/DD/YYYY) ____ / ____ / _____
----------------------------------	-------------------------	---------------------	---

Instructions:

For the following questions about drinking alcoholic beverages, a drink means a 12 oz. beer, a 5 oz. glass of wine, or one and a half ounces of liquor.

1. During the past 30 days, did you drink any alcoholic beverages?

- Yes
- No **(End)**
- Refused **(End)**
- Don't know/Not sure

2. During the past 30 days, how many days per week or per month did you drink any alcoholic beverages, on the average?

_____ (Enter number of days you drank based on the timeframe checked below. Enter 0 if you did not drink.)

- Week
- Month
- Refused
- Don't know/Not sure

3. On the days when you drank, on average, about how many drinks did you have?

_____ (Enter the average number of drinks you had per day.)

- Refused
- Don't know/Not sure

4. In the past 30 days, on how many days did you have 5 or more drinks per day?

_____ Number of times

- None
- Do not know/Not sure

Signature of Individual Completing This Form _____ Date ____ / ____ / ____
(MM/DD/YYYY)

Name of Individual Completing This Form (please print) _____

TOBACCO ASSESSMENT – FOLLOW UP

REGISTERING INSTITUTION	PARTICIPANT ID	VISIT TYPE	VISIT DATE (MM/DD/YYYY)
_____	_____	_____	____ / ____ / _____

1. Do you NOW smoke cigarettes?

- Everyday
- Some days
- Not at all → **Skip to Question 3.**

2. On average, when you smoked, about how many cigarettes do you (or did you) smoke a day? (A pack usually has 20 cigarettes in it).

_____ Number of cigarettes per day

3. How long has it been since you last smoked a cigarette (even one or two puffs)?

First check which one of the following choices applies to you. Then, if applicable, write a number on the line for how many days, weeks, months, or years it has been since your last cigarette.

- I smoked a cigarette today (at least one puff)
- 1-7 days → Number of days since last cigarette _____
- Less than 1 month → Number of weeks since last cigarette _____
- Less than 1 year → Number of months since last cigarette _____
- More than 1 year → Number of years since last cigarette _____
- Don't know/Don't remember

4. Since your last visit, have you used other forms of tobacco, not including cigarettes?

- Yes
- No (**End**)

5. How often do you/did you use other forms of tobacco?

- Every day → Number of times per day _____
- Some days → Number of days _____ per Week Month Year

6. Since your last visit, which of the following products have you used? **Check all that apply**

- Cigarettes
- E-cigarettes or other electronic nicotine delivery system
- Traditional cigars, cigarillos or filtered cigars
- Pipes
- Waterpipe
- Hookah
- Clove cigarettes or kreteks
- Bidis
- Smokeless tobacco, like dip, chew, or snuff
- Snus
- Paan with tobacco, gutka, zarda, khaini
- Other, Specify _____

7. If you do not currently use other forms of tobacco, but did in the past, how long has it been since you last used other forms of tobacco regularly?

- Within the past month (0 to 1 month ago)
- Between 1 and 3 months (1 to 3 months ago)
- Between 3 and 6 months (3 to 6 months ago)
- Between 6 and 12 months (6 to 12 months ago)
- Between 1 and 5 years (1 to 5 years ago)
- Between 5 and 15 years (5 to 15 years ago)
- More than 15 years ago
- Don't know/Not sure
- Never used other forms of tobacco regularly

The following instructions pertain to questions 8 - 10. During each of the following time frames, please indicate whether you smoked cigarettes every day, some days, or not at all.

8. During study treatment

- Smoked every day
- Smoked some days
- Did not smoke at all
- Don't know/not sure
- Not applicable

9. After the end of study treatment

- Smoked every day
- Smoked some days
- Did not smoke at all
- Don't know/not sure
- Not applicable (I have not completed the study treatment)

10. Since your last visit to this clinic

- Smoked every day
- Smoked some days
- Did not smoke at all
- Don't know/not sure
- Not applicable (This is my first visit to this clinic)

Signature of Individual Completing This Form _____ Date ____ / ____ / ____
(MM/DD/YYYY)

Name of Individual Completing This Form (please print) _____

APPENDIX G

Plain Language Guide for Assessing Skin Application AEs

Utilize this guide for assessing Skin Application AEs during the Day 8 phone call and Day 15 and Day 28 visits. To assess skin toxicity please ask the participant non-leading questions such as “Have you noted any changes in the skin of your breast?” If the participant reports yes, then utilize the plain language guide below to ask more probing questions as needed.

1. Is your breast skin dry from gel application? If yes, is it red or itchy?
2. Do you have pain on your breast skin? If yes, how severe?
3. Is your skin itchy from gel application? If yes, how severe? Are you taking any medicine for it?
4. Do you have rash on your breast skin? If yes, how big is the affected area? Are you taking any medicine for it? Can you please send us a picture of your rash?
5. Do you have hives on the breast skin where you have applied the gel? If yes, how big is the affected area? Are you taking any medicine for it?

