5.2 Gel Administration/Run-in Procedures

Each Bexarotene gel canister will contain 30 reliable doses of product metered to dispense 1mL per actuation, 1g of bexarotene gel per actuation. One gram of bexarotene gel contains 10mg of active bexarotene.

Participants in all dose levels will be instructed to apply the gel at 10mg (1 mL) every other day to one unaffected breast for the first 7 days of treatment. After the Day 8 phone call and confirmation that toxicity is at an acceptable range, participants assigned to 10mg/breast/daily will increase applications to daily. Participants assigned to 10mg/breast/every other day will continue to apply gel every other day. Participants assigned to 20mg/breast/daily will increase from 10mg (1mL) every other day to daily application for another 7 days. After the Day 15 visit and confirmation of acceptable toxicity, participants will increase to 20mg (2 mL) to the one unaffected breast daily for the remaining 2 weeks. All participants will continue to apply the gel to one unaffected breast as directed for a duration of 4 weeks. Participants in the dose expansion group will apply the gel with the same ramp up schedule as those in the dose escalation group for that dose level.

Participants will also receive moisturizing lotion [CeraVe] that can be applied to the breast to reduce and prevent redness that can be related from the study drug. CeraVe will be provided to all participants and they will be instructed to apply to the treated breast in the evening or at least 4 hours after application of study drug so it will not interfere with the absorption of study drug.

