11.1 Adverse Events

11.1.1 Reportable AEs

All AEs that occur after the informed consent is signed and baseline assessments are completed (including run-in) must be recorded on the AE CRF (paper and/or electronic) whether or not related to study agent.

11.1.2 AE Data Elements:

The following data elements are required for AE reporting.

- AE verbatim term (Include at application site, if applicable)
- NCI Common Terminology Criteria for Adverse Events version 4.0 (CTCAE v4.0) AE term (MedDRA lowest level term)
- CTCAE (MedDRA) System Organ Class (SOC)
- Event onset date and event ended date

- Treatment assignment code (TAC) at time of AE onset
- Severity grade
- Attribution to study agent (relatedness)
- Whether or not the event was reported as a SAE
- Whether or not the subject dropped due to the event
- Outcome of the event

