11.1.4 Assessment of relationship of AE to treatment

The possibility that the AE is related to study agent will be classified as one of the following: not related, unlikely, possible, probable, definite.

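### Appendix G asks whether dryness or itch comes from the gel, so a truthful no can skip the probes that support the skin grade

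*Combined protocol and SAP*

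**What the plan says.** Skin toxicity is elicited in two steps at the Day 8 call and at the Day 15 and Day 28 visits (Sections 7.3 and 7.4, Appendix G). Staff first ask a non-leading question about any change in the breast skin. If the answer is yes, they use the five items of Appendix G as needed.

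Item 1 reads "Is your breast skin dry from gel application", followed after a yes by a question on redness or itch. Item 3 reads "Is your skin itchy from gel application? If yes, how severe", followed by a question on medicine. Item 2, by contrast, reads "Do you have pain on your breast skin? If yes, how severe" and asks nothing about cause.

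On recording, Section 11.1.1 says that all adverse events after consent and baseline assessment "must be recorded on the AE CRF (paper and/or electronic) whether or not related to study agent". On cause, Section 11.1.4 begins "The possibility that the AE is related to study agent will be classified as one of the following" and lists five levels, from not related to definite. Section 6.9 states that the study is not blinded. Section 5.2 adds a second product on the same skin: "Participants will also receive moisturizing lotion [CeraVe] that can be applied to the breast".

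**The concern.** A question that joins a symptom and its cause has two different reasons for a no: there is no symptom, or there is a symptom that she puts down to something else. The answer does not show which. Soap, clothing and the study's own moisturizer are all causes that a woman could reasonably name.

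The wording can also push the other way. Naming the gel in an open-label study suggests the cause before anyone has classified it, and it departs from the appendix's own instruction not to lead.

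What is at stake is how two of the six rows of Table 3, dry skin and pruritus, are elicited. Safety and toxicity are the primary endpoint, and skin events are expected to be the most common. A grade 2 skin event that lasts at least 6 days, or recurs and lasts at least 3 days, is a dose-limiting toxicity (DLT). The line between grade 1 and grade 2 therefore matters.

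**Working it through.** No formula yields the size of this effect, so the check sets the passages side by side.

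**Step 1. The five items of Appendix G.**

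| Item | Symptom | Asks about cause? | Probes that follow a yes |
|---|---|---|---|
| 1 | Dryness | Yes, the gel | Redness or itch |
| 2 | Pain | No | Severity |
| 3 | Itch | Yes, the gel | Severity, medicine |
| 4 | Rash | No | Area affected, medicine, picture |
| 5 | Hives | No; it asks about the place of application | Area affected, medicine |

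Two of five items carry a causal phrase. The other three show that it is not needed.

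**Step 2. What a no skips.** In Table 3, dry skin is grade 1 without erythema or pruritus, grade 2 with either, and grade 3 with both. The probe behind item 1 asks for exactly that distinction. Pruritus is graded by intensity, by effect on daily activities or sleep, and by topical, oral or oral-steroid treatment. The probes behind item 3 ask for severity and medicine. If she blames another cause for both symptoms, a literal reading of the script passes over both sets of probes.

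**Step 3. Order of recording and attribution.** Section 11.1.1 has the event recorded regardless of cause, and Section 11.1.4 classifies relation on five levels. The DLT definition accepts a possible relation for events of grade 3 or greater. A participant's yes or no on cause, asked first, is a coarser test than the protocol's own and comes at the wrong stage.

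**Step 4. Where other routes of capture are thinnest.** Day 8 is a phone call without an exam. Day 15 and Day 28 include a breast exam, and skin events are photographed. An exam sees what is present that day. The nominal gaps between contacts are 15 − 8 = 7 days and 28 − 15 = 13 days, so an episode of 3 or 6 days can start and end between contacts. For such an episode, and for itch at any time, the record rests on what she reports and on the diary.

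**Step 5. Design figures.** The plan's early-stopping probabilities (Sections 8.1 and 13.4) are the figures that presuppose complete capture of DLTs. Exact enumeration with looks at 3, 6 and 10 participants and then after each from 11 to 20, using boundaries 2/3, 2/6, 3/10, 4/11–14, 5/15–19 and 6/20, gives 15.0%, 51.3% and 82.3% at true DLT rates of 0.10, 0.20 and 0.30. The plan states 15%, 51% and 82%. They reproduce, and rewording two questions changes none of them.

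**The case against.** The strongest reply is that the two items come late and are surrounded by safeguards. They are optional probes, used only after a neutral question has been answered yes, so a skin change is already on the table. Nothing tells staff to drop an event after a no to item 1 or 3. The diary asks daily for any symptoms without asking why, and tells her to call about worrying side effects or a change in skin texture. Section 8.1 has her draw around reddened areas. The follow-up call about 30 days after Day 28 asks again about adverse events. A skin DLT is also hard to miss: it must last or recur, and grade 2 itch is intense, with scratch changes and oral treatment.

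Most of this stands, and it rules out two stronger readings.

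A reader might infer that the woman's guess decides whether an event is recorded and whether it can count as a DLT. The documents do not support that. Recording is required regardless of cause, relation is classified separately, and there are several other routes of capture.

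A reader might also try to express the risk as a loss of stopping probability. Assume a true DLT rate of 30% and that 0, 10, 25 or 50% of all DLTs are missed. The 30% rule of Section 3 would then stop the expansion with probability 79, 74, 64 or 45%. The pooled rule, starting from 0/10, would stop with probability 10, 7, 3 or 1%. The arithmetic is right, but the documents do not support the inputs. They give no missed fraction. The calculation applies it to every DLT, while these items concern two of six skin rows and no non-skin event. A 30% rate also sits poorly with the 0 DLTs in 10 participants reported at this dose in Section 3: at 30%, that result has probability 0.7^10 = 2.8%.

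What survives is narrower. The safeguards do not supply the skipped probes: the diary is free text without a grade, and itch cannot be seen on exam. Item 3 does not repeat the site, but the opening question makes it clear enough, so naming it is only tidiness.

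**Conclusion.** The point holds as a defect of questionnaire wording. Items 1 and 3 can be answered no by a woman who has the symptom, and the grading probes depend on a yes. The wording also conflicts with the appendix's own instruction on non-leading questions and runs ahead of the attribution step. The consequence is a small risk of under-reporting, under-grading or pre-attributing dryness and itch, greatest at Day 8. The net direction is not known, because suggesting the gel may raise reports while asking for cause may lower them.

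This assumes that some participants will name another cause and that staff will read the items as written. The documents do not say how often either happens, so no size can be given. The stopping boundaries, stopping probabilities and sample size are unaffected.

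**What to change.** Delete the words naming the gel from items 1 and 3, and name the site. Suggested wording is *Is the skin of your treated breast dry?* and *Does the skin of your treated breast itch?*, with the existing probes kept after each.

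Add one line to the appendix: symptoms that are new or worse than at the baseline symptom assessment (Sections 7.1 and 7.2) are recorded as adverse events under Section 11.1.1, and cause is left to the classification in Section 11.1.4. The comparison with baseline matters. Recording every yes would also count unchanged dryness that was there before treatment.

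The cost is a change to two questions and one added line. A few more unrelated events may be recorded, which Section 11.1.1 already requires. No analysis or design figure has to be redone.
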